3 STUDY OBJECTIVES & OUTCOMES

To understand the proportion of people with diabetes who experience longer term symptoms or illness after COVID-19 infection, the nature of these symptoms, and the potential health impact of that.

The primary objectives of the study are:

After COVID infection, what proportion of people with type 1 and type 2 diabetes experience symptoms in the longer term (up to 18-24 months after index infection)?

The secondary objectives of the study are:

What is the impact of “long COVID” upon physical activity, diabetes control and outcomes?

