4.4 STUDY MATRIX

The study matrix is shown below.

Case cohort study (online questionnaires):

Approximate Week	Anytime (cases and controls)
Interest to participate	X
Remote Implied Consent (online)	X
Demographic information (online)	X
Questionnaires (online)	X
Option to self-nominate for Nested case control study via provision of contact email and/or phone number (online)	X

Nested case control study (CRF visit):

Approximate Week	-4 to 0	0 (cases and controls)	1 year (40-64 weeks: cases only)
Interest to participate	X		
Inclusion and exclusion assessed by research nurse		X	
Consent (written)		X	
Questionnaires (if not done previously) or repeat of Wellcome section 1.3		X	X
Blood sample for labs (optional)		X	X
Blood sample for routine clinical measures*		X	X
Grip strength test		X	X
Incremental walk test		X	X
Waist and thigh measurement		X	X
Bioimpedance (optional)		X	X
Pulmonary function test** (optional)		X	X
Extract of routinely collected healthcare data from SCI Diabetes system		X	X

*HbA1c, LFTs, lipids, U&Es

**Spirometry/FEV1

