7.2 PROPOSED ANALYSES

An analysis plan will be prepared for the University of Glasgow Research Data Management department before the study closes, to detail what analysis will be performed on the data.

Case cohort study:

This includes **participant completed questionnaires only**. We will not have access to clinical record for whole group (limited to those in nested study) and will rely on patient self-report of COVID testing and infection to create groups. Analysis will be in three groups:

- a. Test positive COVID declared (**cohort A**)
- b. no test but self-declared COVID (**cohort B**)
- c. no COVID infection declared, including those with suspected infection but test negative (**control**)

Analysis of this data will include

1. **Frequency of COVID symptoms** (derived from question 1.3 Wellcome questionnaire: 28 domains answering yes/no for 0-28 score and by self-report at time of infection at 3 months and current (>3 months)).
 - a. **Primary analysis:** current score cohort vs control with adjustment for limited demographic panel: age band, ethnicity, sex, type of diabetes
 - b. Secondary analyses:
 - i. within cohort comparison of time of infection vs 3 months vs current
 - ii. comparison time of infection and 3 months vs current score of control (with adjustment)
2. **Other questionnaire data:** diabetes depression score, DQOL all of which are assessed currently only and will be assessed in cohort vs control.
3. Comparison of above end points in cohort B to cohort and controls.

NESTED CASE CONTROL STUDY

For this data, consent will allow access to confirm that patient is COVID test positive in the clinical record. Definitions and comparison will therefore be between:

Cases - COVID test positive in clinical record

Control - no previous clinical COVID infection reported by patient, no record positive COVID test.

Case vs control (First visit)

1. **Frequency of COVID symptoms** (derived from question 1.3 Wellcome questionnaire: 28 domains answering yes/no for 0-28 score and by self-report at time of infection at 3 months and current (>3 months)).
 - a. **Primary analysis:** current score case vs control with adjustment for age, sex, ethnicity, sex, type of diabetes, SIMD
 - b. Secondary analyses:
 - i. within cohort comparison of time of infection vs 3 months vs current
 - ii. comparison time of infection and 3 months vs current score of control (with adjustment)
 - iii. relationship of cycle threshold to symptom scores

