2. **Other questionnaire data:** diabetes depression score, DQOL all of which are assessed currently only and will be assessed in cohort vs control
3. **Walk test**
4. **Hand grip**
5. **Pulmonary function measures eg. FEV1**

Comparison of cases vs COVID positive cohort for demographics and main study measures.

Case vs control (First and second visit data)

1. **Frequency of COVID symptoms** (derived from question 1.3 Wellcome questionnaire: 28 domains answering yes/no for 0-28 score and by self-report at time of infection at 3 month, at time of first questionnaire, first visit and at second visit).
 - a. **Primary analysis:** second visit score case vs control (first visit) with adjustment for age, sex, ethnicity, sex, type of diabetes, SIMD
 - b. Secondary analyses:
 - i. within cohort comparison of time of infection vs all time points
 - ii. comparison time of infection and 3 months vs current score of control (with adjustment)
2. **Other questionnaire data:** diabetes depression score, DQOL all of which are assessed first and second visit cohort vs control (first visit)

3. **Walk test** first and second visit cohort vs control (first visit)
4. **Hand grip** first and second visit cohort vs control (first visit)
- Pulmonary function measures eg. FEV1** first and second visit cohort vs control (first visit)

B. Screening log. As above contain patient identifiers, will be held on NHS computers.

Output - acceptance rate for study

C. Study data - will be held within Redcaps platform. Outputs: process data on completion of the different modules of the study, final study dataset.

Key aspects will be

- a. Record of consent and electronic consent
- b. Ability to enter data to personal computer/ smartphone by participant
- c. Ability to enter separate data under same study ID for study visit
- d. Cloud exportable to SAS/ SPSS/ R

Analyses will be carried out by the study team using the statistical support offered by the University of Glasgow.

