7.3 MISSING DATA

The online questionnaires will flag incomplete data and will ensure all questions are answered. The questionnaires that are completed on paper or by phone contact may have incomplete sections.

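### Secondary analysis b.ii tests cases' recalled infection and 3-month symptom scores against controls' current score, a difference in measurement that demographic adjustment cannot remove

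*Protocol*

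**What the plan says.** Protocol section 7.2 builds the symptom score from question 1.3 of the Wellcome questionnaire: "28 domains answering yes/no for 0-28 score and by self-report at time of infection at 3 months and current (>3 months"). The cohort questionnaire has a single time point in the section 4.4 matrix, "Anytime (cases and controls"), so a case gives the infection and 3-month answers afterwards, alongside the current ones.

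The same secondary item b.ii then appears in the cohort block, the nested first-visit block and the first-and-second-visit block: "comparison time of infection and 3 months vs current score of control (with adjustment"). The covariates named in section 7.2 are age, sex, ethnicity and type of diabetes, plus SIMD in the nested study.

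The primary analyses are built differently. The cohort primary is "current score cohort vs control with adjustment for limited demographic panel: age band, ethnicity, sex, type of diabetes" and the first-visit primary is "current score case vs control with adjustment for age, sex, ethnicity, sex, type of diabetes, SIMD". The second-visit primary sets cases' second-visit score against controls' first-visit score. None of the three uses a recalled score.

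Two further provisions bear on the 3-month score. Section 4.10 admits nested cases from 10 weeks after a positive test. Section 7.3 says of missing data: "The online questionnaires will flag incomplete data and will ensure all questions are answered"; it allows that paper and phone forms may be incomplete.

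**The concern.** The two sides of b.ii are not the same measurement. A case is asked to reconstruct 28 yes/no symptoms around a remembered illness, perhaps many months back. A control reports today's symptoms, with no index event and no recall period. Any net tendency of cases to over-report or forget past symptoms goes straight into the difference. Age, sex, ethnicity, diabetes type and deprivation do not measure recall accuracy, so adjusting for them leaves that tendency in place.

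At stake is the conclusion drawn from the 3-month contrast. An adjusted comparison with controls invites the reading that COVID raised, or did not raise, symptoms at 3 months. Over-reporting could create such an effect and forgetting could hide one, and the data collected cannot tell which has happened.

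**Working it through.** **1. The plan's own figures (section 7.1).** For two means, two-sided 5% and 90% power, n per group = 2(1.960 + 1.282)²/d².
- d = 0.2 SD: 525.4, rounded up to 526, as stated.
- d = 0.5 SD: 84.1, rounded up to 85, as stated.

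At the planned 500 per group, power is 89% for 50% vs 40% and 93% for 20% vs 12%. The differences the design treats as worth detecting are therefore 10 and 8 points for a single symptom, and 0.2 SD for a score.

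**2. Model for recall error (assumption).** Suppose there is no true difference and both groups have prevalence p. Let f be the share of cases without the symptom who recall it (false yes), and g the share with it who forget it. Then

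recalled prevalence in cases = p(1 - g) + (1 - p)f, and apparent difference = (1 - p)f - pg.

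The inputs p = 40%, f = 5-20% and g = 10-30% are assumed. The protocol gives no recall-error rates.

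**3. Results at p = 40%, 500 per group, two-sided pooled z-test at 5%.**

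| f | g | Apparent difference (points) | Chance of a significant result |
|---|---|---|---|
| 5% | 0 | 0.60 × 5 = +3 | 16% |
| 20% | 0 | 0.60 × 20 = +12 | 97% |
| 0 | 10% | -0.40 × 10 = -4 | 26% |
| 0 | 30% | -0.40 × 30 = -12 | 98% |
| 20% | 10% | 12 - 4 = +8 | 72% |
| 5% | 30% | 3 - 12 = -9 | 85% |
| 12.5% | 20% | 7.5 - 8 = -0.5 | 5% |

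A full 10-point artefact needs f = 10/0.60 = 16.7% with no forgetting, or g = 10/0.40 = 25% with no false yes. For the rarer symptom, f = 8/0.88 = 9.1% with no forgetting turns 12% into 20%.

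**4. On the score itself.** Item b.ii compares a 0-28 score rather than one symptom. If its SD is 3-6 items (assumed), 0.2 SD is 0.6-1.2 items. Divided by 28, that is a net over-report of 2.1-4.3% per item. A recall shift of 0.1 SD with no true difference would be significant 35% of the time at 500 per group.

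**5. Timing.** Ten weeks is shorter than 3 months (about 13 weeks). A nested case attending at 10 weeks has not reached the 3-month point, and section 7.2 defines the current score as beyond 3 months. Yet the online form requires every question to be answered. Sections 4.10, 7.2 and 7.3 do not say what such a case's 3-month or current score means.

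**The case against.** The strongest reply is that b.ii is secondary. The primary analyses use no recalled score, and the primary objective, on longer-term symptoms, does not depend on it. That stands, and it limits the weight of the point.

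Second, the two recall errors oppose each other. Over the assumed ranges together the net never reaches 10 points, and it is about zero at the midpoints. That also stands. A reader might infer that recall error is known to be as large as the target difference; nothing in the documents supports this.

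A reader might also infer that all recall spans 18-24 months and that all answers are forced. Section 3's "up to 18-24 months after index infection" is the outer horizon of the objective, and nested cases may attend from 10 weeks. Complete answers are required online only, and the protocol does not say whether the form has a don't-know option.

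Nor do the documents support rejecting the within-case course, such as the second-visit item "within cohort comparison of time of infection vs all time points". A fall from acute illness is a real change, excess over background is tested elsewhere, and the cohort has no other time points.

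Finally, controls' current score can fairly show the background level of symptoms in diabetes, which section 2 says is needed. That justifies displaying it beside the recalled scores. It does not justify an adjusted test between the two. The promised analysis plan could relabel b.ii, but the protocol itself fixes the comparison in three places and should be corrected there.

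**Conclusion.** The point holds for secondary item b.ii in the cohort, first-visit and second-visit blocks, and not beyond it. Recalled case scores are compared with concurrent control scores, no control score with a matching recall period is described, and the named adjustment cannot repair this.

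The mismatch can be read directly from the plan; its size cannot. Under the assumed 40% prevalence and error ranges, a null 3-month contrast could show anything from +8 to -9 points net, or nothing. The ends of that range are close to the 8 and 10 points in section 7.1 and would be declared significant 72-85% of the time at 500 per group. The b.ii contrast therefore cannot support a statement about a 3-month COVID effect in either direction.

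**What to change.** - In all three blocks of section 7.2, replace b.ii as an adjusted group comparison with a descriptive report of cases' recalled infection and 3-month scores. Controls' current score may be shown as background. State that no 3-month COVID effect will be concluded from it, and that case-control inference rests on current scores.
- In the nested study, where the date of the positive test is needed for the 10-week rule anyway, report by time since infection. Count a 3-month score only for cases at least 3 months past their positive test. Reconcile sections 4.10, 7.2 and 7.3 on this.
- Keep the within-case course (b.i), but label its infection and 3-month points as recalled. For nested cases, present the scores recorded at first questionnaire, first visit and second visit as the main course.

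The cost is wording, with no new data collection. The loss is a formal 3-month case-control test. Reporting by time since infection is asked for in the nested study only, because the cohort data listed in section 6.2 include no infection date.

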4.5 STUDY ASSESSMENTS

Case-Cohort:

Self-completed, offered online (can be offered by phone/on paper for participants who request this).

1. Demographics
2. Questionnaires (in order of priority)
 - a. Wellcome Trust COVID 19 questionnaire (Most up to date version in use at the time of the study): This is a comprehensive instrument covering physical, cognitive, and mental health domains and will also allow comparison to developing UK reference population data). Questions deemed to require additional support have been removed.
 - b. Diabetes Related Quality of Life (DQOL)

- c. Diabetes-Specific [name]-1
 - d. EQ5D
3. Option to self-nominate for nested case control study.

Nested Case Control (CRF visit):

1. Written consent
2. Questionnaires (if not done previously) or Update of symptoms score Wellcome questionnaire section 1.3
3. Blood sample (optional) for research labs (16ml total, 6ml purple top (EDTA), 6ml gold top (serum), 4ml blue top (citrate)) for non-routine bloods: inflammatory (e.g. CRP), vascular (t-PA, vWF) and cardiac (hs troponin, NT proBNP) biomarkers consistently predictive of long-term adverse outcomes.
4. Blood sample (8ml total, 3ml purple top (EDTA) and 5ml gold top (serum)) for routine clinical measures (HbA1c, LFTs, lipids, U&Es).
5. Physical measures
 - a. Incremental walking test
 - b. Grip strength
6. Waist and thigh measurement
7. Bioimpedance (optional if site does not have this equipment)
8. Pulmonary function test (optional if site does not have this equipment)

Cases will be invited to a repeat study visit 1 year (40 to 64 weeks) from the initial study visit.

SOPs (shared from other studies) will be used to standardise:

- Incremental walk test
- Grip strength test
- Blood sampling, storage and shipment
- Pulmonary function test

Clinical data: Baseline and follow up data from SCI-Diabetes including glucose control and blood pressure.

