5 PARTICIPANT SELECTION AND ENROLMENT

5.1 IDENTIFYING PARTICIPANTS

Case Cohort: To allow as wide participation as possible, study instruments (questionnaires) will by default be offered remotely using an online implied consent and completion. For this

reason, we will include only contact details (e mail and or telephone) and limited, broad demographics (age in 5 year categories, ethnicity, sex, type of diabetes, duration of diabetes in 5 year categories, first 4 characters of post code). To be inclusive we will offer support for completion of questionnaires if remote online completion by the participant is not possible.

Nested Case control: This will be with written consent and include CRF visit, physical measures and data linkage to the clinical record for evidence of diabetes complications (current and future).

Case Cohort recruitment:

1. **From Diabetes Research Register:** We will utilise the NHS Research Scotland (NRS) Diabetes Research Network permission to contact research register of people with who have expressed a willingness to be involved in research. This register has a large cohort of people with diabetes (>14,000) who have given permission to be approached directly via email or letter or phone. People with diabetes in Scotland who are part of this system will be approached via email or letter or phone to take part. Remote participation does not require the R&D department permission of the Health Boards as no facility use is taking place. Within the data collected participants will be asked if they have had a positive COVID test or believe that they have had COVID infection.

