6.2 DATA MANAGEMENT SYSTEM

We will use the RedCap data management system (DMS) hosted on a secure server at The University of Glasgow. This system will host all study information with the exception of screening logs and secure link between patient identifiers and study ID - both of which will be held separately on NHS computers. The RedCap platform allows for direct data entry by participants using either personal computer or smartphone.

Data held in NHS – on secure computer in CRF at each recruiting site:

Screening log for invitation to cohort from clinic lists – this will include patient identifiers restricted to CHI, name, telephone number, email address, as well as study process details (date contacted, consent given to send link for questionnaire data).

After written consent a separate file will be maintained with CHI and study ID.

Data held in RedCap (University of Glasgow)

All Cohort study information. This is entered by the participant and includes:

1. Panel of limited demographics (age in 5 year categories, ethnicity, sex, type of diabetes, duration of diabetes in 5 year categories, first 4 characters of post code to allow calculation of SIMD quintile)
2. Contact details (telephone, email address) – optional for participant
3. Study questionnaires (Wellcome, DQOL, DDS-1, EQ5D)

For nested case control study to this will be added:

1. Nested case control screening information recording interest in study/ willingness to attend CRF

After written consent at CRF the following will be added:

2. study ID
3. completed data from CRF visit (incremental walking, hand grip, pulmonary function, waist and thigh measurement, bioimpedence)
4. Participant information including (age to nearest year, ethnicity, sex, type of diabetes, diabetes duration), **e-mail address and/or contact telephone number**
5. Self filled questionnaire
6. Electronic pseudonymised linkage to variables in electronic clinical record being

- a. Sci-diabetes with measures of glycaemia (HbA1c), nephropathy, retinopathy, foot disease
 - b. SMR01 with data on hospital admissions
 - c. Where possible COVID test data for positivity and cycle threshold (cT)
- 7.

The DMS will be based on the protocol and case report form for the study and individual requirements of the investigators. The case report form will collect only information that is required to meet the aims of the study and to ensure the eligibility and safety of the participant.

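### The lead one-year contrast sets cases at their second visit against controls seen only at the first, so calendar-time change and repeat testing are confounded with COVID status

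*Protocol*

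**What the plan says.** Protocol section 7.2 has three analysis blocks: the questionnaire cohort, the nested study at first visit, and the nested study using first and second visit data. Each names its own primary analysis of the 0-28 symptom score from Wellcome question 1.3. In the third block it is "second visit score case vs control (first visit) with adjustment for age, sex", followed by ethnicity, diabetes type and SIMD. For the walk test, hand grip and pulmonary function, the same block lists "first and second visit cohort vs control (first visit"), and the other questionnaires are handled in the same way. For these measures the second-visit contrast therefore stands beside the same-visit one.

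The follow-up schedule is one-sided. The study matrix (4.4) heads the repeat column "1 year (40-64 weeks: cases only"), and section 4.5 states: "Cases will be invited to a repeat study visit 1 year (40 to 64 weeks) from the initial study visit". No second control visit appears anywhere in the protocol.

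Section 7.2 also plans a within-case comparison of symptoms across all time points, as a secondary analysis. It lists no explicit visit 1 to visit 2 change for walk test, grip or FEV1.

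**The concern.** A case-control difference is informative about COVID only if the two groups are otherwise measured under like conditions. Here they are not. By the second visit the cases are 40 to 64 weeks further on, in a study planned for May 2021 to about October 2022, when background conditions for people with diabetes could well change. They have also done the walk, grip and spirometry tests and answered the symptom items before. The controls' single measurement comes before that interval and without prior exposure to the visit tests.

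At stake is how the one-year result is read. A general worsening would look like persistence of COVID effects. A general improvement, or a gain from practice on the walk test, would look like recovery. The direction is not known in advance. Because control follow-up is excluded by design, a later analysis plan cannot supply the missing second-visit control measurements.

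**Working it through.** **Inputs from the protocol.** Planned numbers are 500 cases and 500 controls (4.9, 7.1). The minimum is 100 cases (12.3). Section 7.1 gives 526 per group for 90% power at 0.2 SD, and 85 per group for 0.5 SD, with alpha 0.05.

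**Inputs that are assumptions.** The size of the non-COVID shift between visits and the proportion of cases who return are not in the protocol. Ranges are shown.

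**Step 1: the plan's own figures.** With n = 2(1.960 + 1.282)² / d², d = 0.2 gives 525.4, rounded up to 526, and d = 0.5 gives 84.1, rounded up to 85. Both reproduce, two-sided. Power for 0.2 SD with 500 per group is 88.5%. The sample size calculation is not in question.

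**Step 2: what each contrast estimates.** Let C1 and C2 be the COVID-related difference at visits 1 and 2, T the general change over the interval, and R the repeat-testing effect.

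- Cases at visit 1 minus controls at visit 1 = C1.
- Cases at visit 2 minus controls at visit 1 = C2 + T + R.
- Cases at visit 2 minus the same cases at visit 1 = (C2 − C1) + T + R.

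For the same cases and without adjustment, the second line is the sum of the first and third. It adds no information to them, and it places T + R inside what is presented as a case-control difference. The third line also contains T + R, which is why it must be reported as change and not as a COVID effect.

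**Step 3: what the covariates can do.** Age, sex, ethnicity, diabetes type and SIMD do not carry calendar time or visit number. Age could absorb the year of ageing if age at each visit were used. Section 6.2 lists "Participant information including (age to nearest year, ethnicity, sex, type of diabetes, diabetes duration") among the data added after consent at the research facility and gives no rule for updating it.

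**Step 4: illustration of size.** Take C2 = 0 and a shift of s SD. The standard error is √(1/n₁ + 1/n₂), and the two-sided rejection probability is Φ(s/SE − 1.96) + Φ(−s/SE − 1.96). For s = 0.1 and 500 per group, SE = 0.0632 and s/SE = 1.58, so the probability is Φ(−0.38) plus a negligible tail, or 0.353.

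| Assumed shift (SD) | 500 vs 500 | 400 vs 500 | 350 vs 500 | 100 vs 100 |
|---|---|---|---|---|
| 0 | 5% | 5% | 5% | 5% |
| 0.05 | 12% | 12% | 11% | 6% |
| 0.10 | 35% | 32% | 30% | 11% |
| 0.20 | 89% | 85% | 82% | 29% |

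The bias can also hide an effect. With a true C2 of 0.2 SD and 500 per group, an opposite shift of 0.1 SD cuts power from 88.5% to 35%, and an opposite shift of 0.2 SD leaves 5%.

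**The case against.** The label primary in this block does not make it the study's primary analysis. The stated primary objective is the proportion of people with longer-term symptoms, and the cohort and first-visit nested blocks compare current scores in both groups. For walk test, grip and FEV1 the same-visit contrast is listed too, and a within-case comparison of symptoms is already planned. A reader would therefore see the sound results beside the weak one. All of this stands. It limits the point to the one-year block and lowers its weight.

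Three stronger readings are tempting and are not supported.

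- A reader might infer that ageing is also passed off as a COVID effect. Age is a listed covariate, and using age at each visit would largely deal with it.
- A reader might infer that returning cases are set against the full control group, so that case drop-out biases the result. The protocol says only that controls are taken at first visit. Controls are matched to cases, an analysis plan is to follow, and handling of non-return can properly be left to it.
- A reader might extend the criticism to the secondary analysis described as "comparison time of infection and 3 months vs current score of control (with adjustment"). That is a different matter. Uninfected controls have no infection date from which to count three months, so their current score serves as a background level. The weakness there is recall, not a mismatch of visits.

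The shifts in the table are assumptions, and the 89% is simply the study's own power at 0.2 SD seen from the other side. That is fair: the table shows sensitivity, not expected error rates.

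**Conclusion.** The point holds for the one-year block. The protocol fixes a non-concurrent contrast as its lead analysis of symptoms and lists the same contrast among those for the other questionnaires, walk test, grip and FEV1. Calendar-time change and repeat testing cannot be separated from COVID status in it. The size is not known. With an assumed shift of 0.1 SD, half the difference that section 7.1 uses for its main calculation, a nominal 5% test would reject about 35% of the time at 500 per group and 11% at 100 per group. This assumes no COVID effect and no adjustment; covariates would alter the standard error but would not remove the shift. Repeat testing is most plausible for walk, grip and spirometry; for the symptom score it would be a repeat-reporting effect.

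The defect should be fixed, but it does not undermine the study as a whole: the cohort and first-visit nested primary analyses are unaffected.

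**What to change.** 1. Make within-case change from visit 1 to visit 2 the lead one-year analysis for symptoms, walk test, grip and FEV1, reported as change and not as a COVID effect.
2. Keep the concurrent first-visit contrast as the case-control comparison.
3. Label every contrast of second-visit cases with first-visit controls descriptive. Use age at each visit, and restrict the controls to those matched to returning cases.

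These steps change wording only and use data already planned. The downside is that the one-year block no longer supports a formal case-control claim for symptoms and physical measures.

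Optional: extract one-year HbA1c and blood pressure from SCI-Diabetes for controls as well as cases. Section 5.1 already places "data linkage to the clinical record for evidence of diabetes complications (current and future") under the nested study's written consent, and section 4.5 names follow-up glucose control and blood pressure, although the matrix puts the one-year extract in the cases-only column. This gives a concurrent contrast for those two measures and repairs nothing else.

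Re-sending Wellcome section 1.3 to controls would give concurrent symptom data, but it is an added assessment. It would need an approved amendment and a rule for controls infected in the interval, since section 5.3 moves controls found to be cases into the case arm. It is not part of the core fix.

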2. **From diabetes clinic lists or database search (SCI Diabetes):** To augment recruitment of COVID test positive participants we will also screen clinic lists and recruit directly. A member of the study team will screen diabetes clinic lists (eg trak or local clinical system, when possible SCI Diabetes) which routinely have a note of previous COVID infection. Name and CHI noted on screening log (excel spreadsheet held on NHS computer). If patient declines this is noted and no further action. If patient assents to contact then contact information taken (telephone and email – if neither possible postal address) and added to screening log. Electronic data collection link sent by preferred means. If electronic remote data collection not possible then paper questionnaires will be made available by post or study team will discuss over the phone. Cases identified to by SCI Diabetes search will be approached in writing with Caldicott Guardian approval in place within a Health Board (likely to be used in selected Health Boards only).
3. We will also advertise the study by leaflets and posters and via newsfeed to My Diabetes My Way, allowing self-referral to the study team.

NESTED CASE-CONTROL RECRUITMENT:

Cases, by definition, will have had a positive COVID test present on the clinical record. Potential cases will be selected from the cohort where a record of self-reported COVID infection is presented. Potential cases will be invited to CRF visit by telephone or email. Where assent is given by phone the clinical record will be checked to confirm positive COVID test, visit is arranged, and PIS sent. All other study procedures will take place only after face-to-face written consent is obtained at the CRF visit.

Controls will be selected from the pool of people who have completed the online questionnaire information and who have indicated that they have not had a **positive** COVID test and do not believe that they have had COVID infection. Those who had possible infection but subsequent test negative are included. Matching will be by age (5 year category),

ethnicity, sex, SIMD quintile and type of diabetes included in the participant completed questionnaire.

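### Section 7.2 plans a second-visit comparison of DQOL and a diabetes depression score, but the visit schedule does not repeat these questionnaires at one year for cases who have already completed them

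*Protocol*

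**What the plan says.** Protocol section 7.2, in the block on first- and second-visit data of the nested study, has an item for other questionnaire data: "diabetes depression score, DQOL all of which are assessed first and second visit cohort vs control (first visit". This sets cases at both visits against controls at their only visit.

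The matrix in section 4.4 has one questionnaire row for the nested study, marked at week 0 and at one year: "Questionnaires (if not done previously) or repeat of Wellcome section 1.3". Section 4.5 gives the same rule for the research-facility visit: "Questionnaires (if not done previously) or Update of symptoms score Wellcome questionnaire section 1.3". It adds: "Cases will be invited to a repeat study visit 1 year (40 to 64 weeks) from the initial study visit".

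The instruments are listed in section 6.2: "Study questionnaires (Wellcome, DQOL, DDS-1, EQ5D". In section 4.5, "Diabetes Related Quality of Life (DQOL" and the other instruments appear under the online case-cohort assessments, and none has its own line among the visit assessments.

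On the source of nested cases, section 5.1 says: "Potential cases will be selected from the cohort where a record of self-reported COVID infection is presented". On controls it says: "Controls will be selected from the pool of people who have completed the online questionnaire information".

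**The concern.** The analysis section treats DQOL and the diabetes depression score as measured at the second visit. The schedule, which is what sites work from, repeats only the symptom section for anyone who has already filled in the questionnaires. If the schedule governs, a listed analysis has no second-visit data on the case side.

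The analysis plan that section 7.2 promises before the study closes cannot repair this, because it cannot supply answers that were never collected. Each one-year visit held under the present schedule is a lost opportunity for these scores.

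There is also a smaller naming problem. Diabetes depression score matches none of the instruments listed in section 6.2, so the analysis item cannot be traced to a form without an assumption.

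**Working it through.** The plan gives no figure on this point, so the check compares what 7.2 needs with what 4.4 and 4.5 schedule.

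**Step 1. What the analysis needs.** For cases: DQOL and the depression score at the first and at the second visit. For controls: the same scores at the first visit.

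**Step 2. What each case receives under the either/or rule.**

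| Route | Online | First visit | One-year visit | Second-visit DQOL or depression score |
|---|---|---|---|---|
| A. Set completed online | full set | section 1.3 | section 1.3 | none |
| B. Set not done online | – | full set | section 1.3 | none |
| C. Set done neither online nor at the first visit | – | missed | full set | yes, but no earlier value |

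Section 5.1 draws cases from the questionnaire cohort, so route A should be the usual one. Route B is the fallback that 4.4 and 4.5 provide. Route C requires the first-visit assessment to have been missed. On no route does a case have these scores at both visits.

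**Step 3. The control side.** Controls have no second visit, and 5.1 selects them from people who have completed the online form. Their comparison values therefore exist. The gap is on the case side, at one year.

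**Step 4. Does it matter which instrument is meant?** If the diabetes depression score is DDS-1, it belongs to the set that is not repeated. If it is drawn from the mental-health content of the Wellcome questionnaire, it is still not repeated unless it lies within section 1.3, which 7.2 describes as 28 yes/no symptom items. The conflict therefore does not depend on equating the score with DDS-1, and for DQOL no such question arises.

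**Step 5. The other items in the same block of 7.2.**

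| Second-visit item in 7.2 | Scheduled at one year in 4.4? |
|---|---|
| Symptom score (Wellcome 1.3) | yes |
| Walk test | yes |
| Hand grip | yes |
| Lung function | yes (optional) |
| DQOL, diabetes depression score | only if the set was not done previously |

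Only the last row lacks a data source for cases who have followed the schedule.

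**The case against.** The strongest reply is that section 7.2 itself says these scores are assessed at both visits, so two statements conflict and the protocol does not say which governs. Other text leaves room for a repeat: the questionnaire row is marked at one year, section 4.2 has cases repeating the facility visit, section 6.2 adds a self-filled questionnaire after written consent, and 7.2 asks that the database accept separate visit data under one study ID. Section 7.3 also allows that paper or telephone forms may be incomplete, so not everyone need have finished the set. This stands as far as it goes: a reader might infer that the second-visit data certainly will not exist, and the documents do not support that. But none of these places names DQOL or a depression instrument, and what is repeated at one year is the visit as 4.4 and 4.5 define it, including the either/or rule.

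Four further readings go beyond the text.

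- *A one-year change in quality of life is lost.* For these scores 7.2 words the comparison as cases against first-visit controls. Within-cohort comparison over time is listed only for the symptom score.
- *A main outcome is lost.* The synopsis names the walking test, hand grip and HbA1c as secondary measures. DQOL and distress are not among them.
- *First-visit scores are out of date because they come from the online form.* No interval between online completion and the visit is given, and using the online value is a design choice.
- *EQ5D is missing from the analysis list.* It can be dealt with in the analysis plan and is not an error here.

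**Conclusion.** The conflict is real but limited. Section 7.2 requires second-visit DQOL and depression scores in cases, and sections 4.4 and 4.5 do not schedule them for cases who have already completed the questionnaires.

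The conclusion rests on two assumptions: that sites follow 4.4 and 4.5 as written, and that cases have completed the set online or at the first visit, as the recruitment route and schedule intend. Under these, no such case has a second-visit value, and the second-visit comparison cannot be made for them. The number affected cannot exceed the cases who return, out of a planned 500. The protocol does not say how many would return or how many might reach one year without having done the set.

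The damage is confined to one line of other questionnaire data. It should be settled before more one-year visits are held, since the missing answers cannot be recovered later.

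**What to change.** Reconcile 7.2 with 4.4 and 4.5 in one of two ways.

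1. **Collect the data.** Amend the questionnaire row in 4.4 and the matching item in 4.5 so that returning cases complete DQOL and the depression/distress instrument at the one-year visit, whether or not they have done them before. The cost is a slightly longer questionnaire for returning cases, on forms already in the REDCap system, plus an amendment approved as section 12.1 requires.
2. **Drop the analysis.** Delete the second-visit comparison of these scores from 7.2. This adds nothing to collection but gives up the one-year case-control comparison on them.

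In either case, state in 7.2 which listed instrument the diabetes depression score refers to. DDS-1 is the likely candidate, but that is an inference for the sponsor to confirm.
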